9.2.1 Primary outcomes

- To examine the efficacy of piano training to improve CAP, cognition, and everyday function among older adults. We will assess the effects of piano training as compared to music listening instruction on CAP, cognition, and everyday function.

CAP includes Time Compressed Speech, Words-in-Noise, Dichotic Digits Test, Dichotic Sentence Identification and Adaptive Tests of Temporal Resolution. All are parametric tests of perception.

Cognition includes Verbal Fluency (phonemic, category, and switching), Digit Coding, and Trail Making test. All are parametric tests of cognitive function.

Everyday function includes the Timed IADL test and Test of Everyday Attention both parametric measures. Both measures will be examined individually.

Principal Component Analyses (PCA) will be performed with CAP, cognitive and functional measures to form composites of outcomes for use in analyses to reduce the number of comparisons.

Hypotheses: The piano training group will outperform the music listening instruction group on measures of CAP, cognition, and everyday function immediately post-intervention.

Secondary Objectives

The secondary objectives are:

- To examine the moderating effects of MCI on piano training efficacy. Moderating effects of MCI status will determine if piano training is effective for older adults with and/or without MCI. We do not have a directional hypothesis for this objective.
- To explore mediators of intervention effects.

Hypothesis: Grounded in theory⁸ and prior research⁹⁻¹¹, we hypothesize that piano training will improve CAP and cognitive performance, leading to functional improvements. We expect that enhanced CAP will mediate cognitive gains. We further hypothesize that cognitive gains will mediate functional improvements.

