9.3 Sample Size

We expect up to 20% attrition after the initial in-person visit across the time period in which cognitive intervention study protocols will be administered. Our goal is to complete in-person screening visits for up to 450 participants in order to have up to 360 participants complete the study. We can tolerate higher rates of attrition. We require a minimum of 198 eligible participants with *at least* 99 individuals randomized to each condition (piano training, controls) to have adequate statistical power. With stratified randomization, this will result in *at least* 48 persons per MCI/no MCI subgroup.

Statistical power analysis using G*Power¹²³ in consideration of our pilot data effect sizes as well as attrition was conducted to estimate power. We will control type I error at .05 to achieve at least 80% statistical power.

To power **Specific Aim 1: To examine the efficacy of piano training to improve CAP, cognition, and everyday function among older adults**, a final n of 198 participants ($n=99$ per randomized condition) will achieve 95% power to detect a significant group x time interaction across baseline to immediate post-test, with an alpha of .05. This assumes a small effect size (f) of 0.10¹²⁴ (Cohen's f effect sizes are 0.10- small, 0.25- medium: f is roughly equivalent to $\frac{1}{2}$ of d when comparing two groups)¹²⁴.

To power **Specific Aim 2: To examine the moderating effects of MCI on intervention efficacy**, a final n of 168 will have .95 power at alpha .05 to detect medium effects ($f=.10$) for significant group x time x moderator three way interactions.

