Specific Aim 1: To examine the efficacy of piano training to improve CAP, cognition, and everyday function among older adults. We will compare changes in performance for piano training relative to control across the two measurement points (baseline, immediate post-test). We will use the PCA-derived composites of CAP and cognition, and everyday functioning as outcomes. We will use repeated measures analyses of variance within the mixed effects models, examining group as the between-subjects factor and time as the within-subjects factor. The group x time interaction will indicate whether the participants randomized to piano training change at differential rates over time relative to those randomized to the control group. This output will be obtained for each of the composite outcomes (CAP, cognition, and functional abilities). For aim 1 analyses and the composite outcomes of CAP, cognition, and everyday function, we will apply Holm-Bonferroni adjustments¹²⁵ to reduce Type I error. Specifically, the Holm-Bonferroni procedure uses a step-down process whereby p-values are sorted from lowest to highest, then the lowest p-value is used in its raw version, the second lowest p-value is multiplied by two, the third lowest p-value is multiplied by three and so on until the adjusted

p-value reaches or exceeds the pre-specified threshold for statistical significance, in our case a two-tailed p value of .05.

Intent-To-Treat Approach. We expect that some participants will not complete their intended followup according to the protocol for a variety of reasons, generating missing values. Intent-to-treat (ITT) analysis has become a widely accepted method for dealing with this issue. To maximize available information, we will employ statistical techniques that allow for the inclusion of missing data. Specifically, we will use linear mixed effects models to analyze data. This advanced analytical method allows for the inclusion of participants with missing data, so long as data are missing at random and offers flexibility with regard to the specification of the variance/covariance structure, which often leads to improved fit of the analytical model to the actual data. If there is non-ignorable missing data, we will apply pattern-mixture mixed effects models to assess the sensitivity of our findings with regard to missing data¹²⁶.

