The randomized groups did not differ in sex, $\chi^2(1)=.787, p=.375$, ethnicity $\chi^2(1)=.167, p=.683$, or race, $\chi^2(1)=.045, p=.832$. The Music Reading Assessment scores did not differ between the two groups, $t(266)=-.958, p=.338$. The randomized groups did not significantly differ in age, $F(1,266)=.293, p=.589$, education, $F(1,266)=.369, p=.544$, MoCA, $F(1,266)=.427, p=.514$, or GDS, $F(1,266)=.943, p=.332$. However, there were marginally significant group differences for PTA in the left ear, $F(1,266)=3.31, p=.070$ and statistically significant group differences for both PTA in the right ear, $F(1,266)=6.69, p=.010$, and visual acuity, $F(1,266)=8.99, p=.003$. The music listening group tended to have worse hearing, while the piano training group tended to have worse visual acuity. See Table 1. The groups also differed significantly in their expectations regarding potential benefits of their randomized group, $F(1,214)=15.07, p<.001$. The piano training group had an average rating of 5.55 while the music listening group had an average rating of 4.99, indicating the piano training condition had higher expectations about the potential effects of their randomized condition. The piano training group also rated their condition as more challenging with 92% agreeing that the intervention was challenging as compared to 86.3% of the music listening group indicating their condition was challenging ($p<.001$).

Principal component analysis with varimax rotation was conducted to reduce the number of variables for analyses. Please see Supplemental Table A for details. The first factor reflected cognitive performance speed and included the Trail Making Test, Digit Coding, and the TEA visual elevator and phone search subtests. The second factor included all three verbal fluency subtests. The third factor reflected CAP and included DDT, DSI, TCS, and WIN. The fourth factor included two indices from the TEA phone search while counting and visual elevator accuracy. The fifth composite included ATTR across- and within- channel performance. Baseline composites of cognitive performance, verbal fluency, ATTR, CAP, and everyday function were created by averaging z scores after the reverse-scaling of items with negative factor loadings. Post-test scores were standardized

by baseline means and *SDs*. Timed IADL performance did not significantly load on any factor and was thus examined separately.

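### The Holm-Bonferroni steps for the Aim 1 composites are written in reverse order; followed literally, they allow a family-wise error rate of up to about 14% instead of 5%

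*Combined protocol and SAP*

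**What the plan says.** Section 9.3 sets the overall target: "We will control type I error at .05 to achieve at least 80% statistical power". Section 9.6 (Specific Aim 1) tests a group-by-time interaction on each composite: "This output will be obtained for each of the composite outcomes (CAP, cognition, and functional abilities". For this family it states "we will apply Holm-Bonferroni adjustments", cites a reference for the method and calls it a step-down process.

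It then sets out the steps. Once the p-values are ranked in ascending order, "the lowest p-value is used in its raw version, the second lowest p-value is multiplied by two". A factor of three follows for the next one, continuing in this way, and the procedure ends when an adjusted value is no longer below the threshold, which is given as "in our case a two-tailed p value of .05".

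The size of the family is not settled. Section 9.6 speaks of three composites but lets the principal component analysis decide how many there are. Section 9.2.1 says of the Timed IADL and the Test of Everyday Attention: "Both measures will be examined individually". Section 14 (Results) reports that "Timed IADL performance did not significantly load on any factor and was thus examined separately", and Table 14.2 shows six outcomes.

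**The concern.** Holm's procedure protects the first rejection most heavily, because that is where a false positive is likeliest when nothing is truly different. The written steps remove this protection. The smallest p-value is compared with .05 as it stands, however many composites are tested, and the penalties fall on the later p-values, where Holm relaxes them.

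This is the only formal p-value adjustment in the plan. Aim 2, the mediation analysis and the exploratory subgroup analyses all use an alpha of .05. A false first rejection would also spread: Section 9.6 makes the mediation analysis depend on significant Aim 1 effects, and Section 9.8 examines sex as a moderator of significant Aim 1 or Aim 2 effects.

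The text also names one method and describes another. That leaves two decision rules available once the data are seen, and they can disagree.

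**Working it through.** **Inputs.** Two-sided alpha .05 and three composites (Section 9.6, Specific Aim 1). Multipliers as written, smallest to largest p: 1, 2, 3. Holm's multipliers for m = 3: 3, 2, 1. The documents give no correlation between the three test statistics, so it is an assumption here, varied from 0 to 0.9.

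**Does the written rule give the stated 5%?** When all three null hypotheses are true, a first rejection occurs whenever the smallest raw p is below .05. For independent tests:

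- Written rule: 1 − (1 − 0.05)³ = 1 − 0.8574 = 14.26%. The union bound is 3 × 0.05 = 15%.
- Holm: 1 − (1 − 0.05/3)³ = 4.92%.

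The stated 5% is not reproduced by the written rule; it is met by Holm.

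**Correlated statistics, all nulls true** (simulation, 1,000,000 draws, equicorrelated normal statistics, two-sided):

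| Correlation | Written rule | Holm |
|---|---|---|
| 0 | 14.3% | 4.9% |
| 0.1 | 14.2% | 4.9% |
| 0.3 | 13.6% | 4.8% |
| 0.5 | 12.5% | 4.4% |
| 0.7 | 10.9% | 3.9% |
| 0.9 | 8.4% | 3.0% |

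**Some effects real (independent tests).**

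- One composite with a very strong effect: it takes the first rank, and the smaller of the other two p-values is doubled under either rule. The error rate is 1 − (1 − 0.025)² = 4.94% under both.
- Two composites with very strong effects: the remaining p is tripled as written, giving 0.05/3 = 1.67%; Holm leaves it unadjusted, giving 5.0%.

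The inflation therefore arises when no composite has a strong real effect. When two do, the written rule is needlessly strict for the third.

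**Larger families.** The written first step ignores m. For independent tests with all nulls true, 1 − 0.95^m gives 18.5% for four, 22.6% for five and 26.5% for six (about 24% for six at a correlation of 0.3). Holm stays just under 5% for four, five and six independent tests. The six-test figure is hypothetical: Section 14 does not say what adjustment, if any, was applied to the six outcomes.

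**Two worked examples (m = 3).**

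- p = .04, .30, .60. Written: .04 × 1 = .04, declared significant. Holm: .04 × 3 = .12, not significant.
- p = .001, .012, .03. Written: .001, .024, .09, two rejections. Holm: .003, .024, .03, three rejections.

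**Reported data.** The group-by-time p-values in Table 14.2 are .265, .327, .515, .638, .763 and .765. The smallest exceeds .05 before any adjustment, so neither rule rejects anything.

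**The case against.** Four points can be made for the plan.

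- **The named method is right.** Section 9.6 names Holm-Bonferroni and cites a source. An analyst using a standard software routine would get correct Holm, with control at 5%. This stands as far as it goes: the 8% to 14% applies only if the written steps are followed. But those steps are offered as the specific definition of the procedure, no other section corrects them, and Section 14 does not say which was used.
- **The figure of 14% is the unfavourable end.** It needs all three nulls true and nearly independent statistics. This is correct, and the range is given above for that reason. Every value in it still exceeds 5%, and family-wise control is meant to hold when all nulls are true.
- **Cognition is called the primary outcome of interest** (Sections 1.3 and 2.1). Since every written multiplier is at least 1, the error rate for any single composite never exceeds 5%. This is true for cognition alone. However, Sections 9.2.1 and 9.6 place all three domains under the primary aim, adjust them as one family and set no hierarchy, so the family-wise rate is the relevant one.
- **The trial is finished and null.** Accepted: no reported conclusion changes. The defect lies in the prespecified rule, which was invalid however the data fell.

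**Conclusion.** The concern holds. Section 9.6 reverses Holm's multipliers, and the rule as written does not deliver the .05 control promised in Section 9.3. With three composites and no true effects, the family-wise error rate is 14.3% if the test statistics are independent and 8.4% at a correlation of 0.9; correct Holm is at or below 5% in every case examined. These figures assume that the written steps are applied literally and that the family has three members; a larger family makes the inflation worse. With two strong real effects the error goes the other way, testing the third composite at 1.67% instead of 5%. The error in the text is certain, and its size depends on the unstated correlation. The published null finding is unaffected.

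**What to change.** Replace the description of the steps in Section 9.6 with wording such as: *With m composites, multiply the smallest p-value by m, the next by m − 1, and so on down to 1 for the largest. Make the adjusted values non-decreasing, and stop at the first that is .05 or more.* State m as the number of outcomes actually tested under Aim 1: three as planned, six as in Table 14.2. Reconcile this with the statement in Section 9.2.1 that the two everyday function measures are examined separately. Because the trial is complete, issue this as a dated correction and say which rule, if any, was applied to the reported p-values.

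The wording costs one sentence. The statistical price is that the smallest p-value must fall below .05/m instead of .05. For the Section 9.3 scenario (N = 198, f = 0.10), the noncentrality is f² × N × 2/(1 − ρ), where ρ is the baseline to post-test correlation, which the plan does not state. At ρ = 0.7 this is 0.01 × 198 × 2/0.3 = 13.2, and power is 95.1% at alpha .05, matching the plan's 95%. At the first Holm step for three tests (.05/3 = .0167) it is 88.7%. If ρ is 0.5, the two figures are 80.0% and 65.5%. This reduction already follows from the method the plan names; the correction only makes it visible.

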Those potentially eligible based on completion of these measures will further complete baseline cognitive, CAP, and everyday functional measures.

Those eligible who score 26³ or better on the MoCA will be enrolled in the study and referred to the study coordinator for randomization.

Those potentially eligible who score between 20 to 25 on the MoCA who were not referred by the MDC or study physician will also complete a clinical evaluation visit. A cut-point of 20-25 on the MoCA is indicative of probable MCI, while less than 20 is suggestive of dementia⁸⁸.

³ The MoCA cutpoint was changed from 27 to 26 to use the more traditional and accepted value for impairment. Those who score between 20 to 25 will complete the clinical evaluation, rather than those who score 20 to 26.

The purpose of the clinical evaluation is to determine if participants have MCI or dementia. The clinical evaluation visit will include subtests of the National Alzheimer's Coordinating Center Uniform Data Set (NACC) neuropsychological battery and an exam by a study physician. Subtests of the NACC battery will be used to determine MCI status and exclude dementia. The NACC battery subtests to be administered include the Clinical Dementia Rating Scale, the Multilingual Naming Test, the Benson Complex Figure Copy immediate and delayed subtests, the Craft Story 21 immediate and delayed recall subtests, Functional Assessment Scales, and Clinical Diagnosis Form, completed by a study physician who is a geriatric psychiatrist.

An exception to the above procedure will be for patients with MCI who were referred from the USF Health Memory Disorders Clinic (MDC) or a study physician who have already undergone clinical evaluation in the past 6 months. Eligible and enrolled participants referred from the clinic with prior MCI diagnosis and evaluation in the clinic completed within the past 6 months will be referred to study coordinator for randomization.

In replicate 1 and later replicates, we plan to request lab results from the past year from those who score 20-25 on the MoCA. The purpose is to rule out medical causes of cognitive decline that are treatable. If copies of lab results are not obtained at the baseline visit, we will request that the participant complete a release of medical records. If we do not receive medical records by the clinical evaluation, and the study physician recommends it, we may draw blood and order lab tests that may include:

- CBC
- Metabolic panel

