5.5 Describe the procedure for obtaining intervention group assignment

The study coordinator with the statistician will randomize participants stratified by MCI status. Participants with and without MCI will be randomized in a 1:1 ratio to either piano training or the active control condition of music listening instruction. To ensure balance throughout enrollment, randomization will be stratified by MCI status (present vs. absent) and conducted in varying blocks of participants as designed by Co-I Ji. [name] will generate the stratified permuted random blocks using R. [name] will maintain the random seed and the computer codes and will send the randomization list to the clinical trial coordinator. The treatment allocation will be denoted as A or B and recorded on the randomization form by the clinical trial coordinator. The study coordinator will control access to the randomization list and know whether A (B) stands for intervention (control). Study investigators [name], [name], and [name] will remain blind to participant condition. The testers will remain blind to participant condition. The trainers (including Co-I [name]) and clinical trial coordinator will be aware of participants' randomized condition.

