C=covariate, E=exploratory, I/E=inclusion/exclusion, IV=internal validity, O=outcome, R=regulatory, SC=sample characterization							

6.1 *Timing of Evaluations*

Prior to Randomization: The baseline visit should be scheduled within 60 days of the telephone screening interview. Informed consent must be obtained first at the baseline study visit prior to any data collection. The GDS, MoCA, Music Reading Assessment, as well as hearing and vision screenings must be completed at baseline, prior to the clinical evaluation. The central auditory processing measures, cognitive assessment battery, everyday functional assessments and health questionnaire should be completed at baseline, but missing items can be administered at the beginning of the clinical evaluation, if needed. The clinical evaluation should be completed within 45 days of the baseline visit completion. The NACC assessments will be completed at the clinical evaluation. All the aforementioned measures for the baseline and clinical evaluations should be completed prior to randomization and must be completed prior to the training content being administered. It will be allowable to administer any of the aforementioned measures that are missing from the baseline or clinical visits after randomization, but administration will not be allowed once the participant has received any piano or music listening training.

Prior to Training Content: Any biomarker assessments must be completed prior to training content (blooddraw, mri, etc.). The general and music self efficacy measures can be administered at either baseline or after randomization on day 1 of training, but must be administered prior to participants receiving any piano- or music listening- content training. If the basic piano or music listening measures are administered prior to randomization, the participant will be withdrawn from the trial and a protocol deviation will be noted. The pre-training basic piano and music listening measures must be administered after randomization and must be administered before training content is delivered. If any of the aforementioned baseline, clinical, or pre-training measures are administered after the training content began, a protocol deviation will be noted. Such measures will be coded as missing and will not be used in analyses.

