Specific Aim 2: To examine the moderating effects of MCI on intervention efficacy. We will also test for moderation effects to determine at what stage along the cognitive status continuum—without MCI vs. MCI—intervention is most effective. To do so, we will examine three-way interactions (MCI x training group x time) for the CAP, cognitive, and everyday function composites. When an interaction is significant, we will stratify analyses by MCI status and examine effect sizes. Effect sizes from pre- to post- training relative to controls will be compared for participants with/without MCI. An alpha of .05 will be used for these analyses.

Participants who score 26 or higher on the MoCA will be defined as no MCI (i.e., cognitively normal). Those participants who score a 20-25 on the MoCA will be defined as MCI if they score a 0.5 on the CDR and have performance at or 1 SD below their age, sex, and education norms on any of the following measures: Trails, Verbal Fluency, Digit Coding, Craft Story Recall, Multilingual Naming Test, or Benson Complex Figure. Those with MoCA scores 20-25 who score 0 on the CDR, but have performance at or 1SD below expected for age, sex, and education will be adjudicated prior to analyses. If an individual scores 20-25 on the MoCA, and 0.5 on the CDR, but has performance above expected on all of the aforementioned measures, their case will be adjudicated prior to analyses. The study physicians will adjudicate such cases prior to coding of MCI status for final analyses.

To quantify the effects of piano training further, in addition to examining composite outcomes as detailed above, we will calculate and report effect sizes for pre-to-post change of piano training relative to controls for each individual measure of CAP, cognition, and everyday function for the sample overall as well as stratified by MCI status and among those who were adherent only (80% or more of sessions completed).

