expectations about the assigned condition were significantly related to composite outcomes of CAP and cognition. However, having greater expectations that the randomized condition would positively affect abilities was associated with poorer performance. See Table 2. Additional sensitivity analyses examined if there were differential effects by sex. No significant group-time-sex interactions were evident ($p > .119$), and the pattern of results was the same when analyses were stratified by sex.

Table 14.1. *Participant characteristics by randomized arm and cognitive status.*

Cognitive status	Piano Training		Music Listening	
	Non-MCI	MCI	Non-MCI	MCI
	M (SD)	M (SD)	M (SD)	M (SD)
	n (%)	n (%)	n (%)	n (%)
Age in years	69.1 (5.5)	71.4 (7.1)	69.6 (5.2)	72.1 (5.7)
Education in years	16.0 (2.3)	16.5 (2.2)	16.0 (2.1)	15.4 (2.3)
Sex (% female)	63 (65%)	18 (48%)	58 (59%)	17 (44%)
Music Reading Assessment score (/40)	2.52 (4.31)	2.43 (3.83)	3.42 (5.41)	2.08 (4.29)
Montreal Cognitive Assessment score (/30)	26.6 (2.1)	23.3 (1.4)	26.6 (1.9)	22.8 (1.6)
Geriatric Depression Scale short-form score (/15)	0.9 (1.2)	1.1 (1.1)	0.9 (1.1)	0.6 (0.9)
Pure tone average left ear (dB)+	19.8 (9.4)	20.4 (9.4)	20.9 (10.8)	27.7 (15.9)
Pure tone average right ear (dB)+*	18.6 (10.3)	20.4 (9.9)	22.4 (14.0)	25.8 (11.6)
Visual acuity (logMAR)+*	.04 (.12)	.09 (.15)	.01 (.13)	.01 (.10)
Expectations (rating/7)*	5.4 (1.2)	5.8 (0.8)	4.9 (0.8)	5.3 (0.8)

Note. MCI=mild cognitive impairment. +Lower scores reflect better performance. *Significant differences by randomized group were evident in pure tone average right ear, visual acuity, and expectations ($ps<.01$).

Table 14.2. *The effects of randomization to piano training as compared to music listening from baseline to post-training across composite outcomes of central auditory processing, cognition, and everyday function.*

	Estimate	SE	p	Estimate	SE	p
	ATTR+			Central auditory processing		
Intercept	53.90	1.17	<.001	46.25	0.73	<.001
Group	-2.24	2.37	.346	-1.72	1.49	.249
Time	-2.77	0.68	<.001	2.29	0.36	<.001
Group x time	1.51	1.35	.265	.465	0.71	.515
Hearing	0.12	0.06	.030	-0.63	0.04	<.001
Visual acuity	6.24	4.71	.187	-7.270	3.97	0.07
Expectations	0.79	0.59	.185	-1.20	0.49	.016
	Verbal fluency			Cognition		
Intercept	49.32	0.98	<.001	51.81	0.90	<.001
Group	-1.81	2.00	.367	-2.62	1.84	.157
Time	0.41	0.48	.393	-1.40	0.42	.001
Group x time	-0.29	0.96	.763	0.39	0.84	.638

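### The MCI coding for Aim 2 is not tied to the MCI stratum used at randomisation and can differ from it, and the stratum itself enters no planned model

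*Combined protocol and SAP*

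**What the plan says.** **Status at randomisation.** Section 5.5 provides that "randomization will be stratified by MCI status (present vs. absent) and conducted in varying blocks of participants", and that "Participants with and without MCI will be randomized in a 1:1 ratio". The rule behind the stratum is not written out, but its sources are. Participants with a MoCA of 26 or more go straight to randomisation (Section 5.3). Those scoring 20 to 25 have a clinical evaluation, where "Subtests of the NACC battery will be used to determine MCI status and exclude dementia" and a study physician completes a diagnosis form; Section 6.3.2 places this visit before randomisation. There is also a referral route: "Eligible and enrolled participants referred from the clinic with prior MCI diagnosis and evaluation in the clinic completed within the past 6 months" are sent for randomisation without the study's own evaluation.

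**Status in the analysis.** Section 9.6 (Specific Aim 2) sets its own rule. A MoCA of 26 or more is no MCI. A MoCA of 20 to 25 is MCI if the CDR is 0.5 and at least one listed test is at or 1 SD below norms. Two discordant patterns go to adjudication: CDR 0 with a test deficit, and CDR 0.5 without one. On these the plan says: "The study physicians will adjudicate such cases prior to coding of MCI status for final analyses".

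**Models.** For Aim 1, Section 9.6 names group and time as factors. Covariates are added only if the arms differ at p < .1 on a list that includes MoCA but not MCI status. The sensitivity analyses in Section 9.7 deal with missing data and outliers. The randomisation stratum is in none of these.

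**The concern.** The sample-size text in Section 9.3 derives the size of the MCI and non-MCI subgroups from stratified randomisation, so it treats stratum and analysis subgroup as one variable. Section 9.6 defines the analysis subgroup afresh and never says that the two agree. Three things follow.

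1. Balance by arm is guaranteed within the strata, not within the groups that Aim 2 compares.
2. The final coding of some participants is left to a judgement whose only stated deadline is before the analyses. No blinding to arm or post-test scores is stated, and nothing confines adjudicators to baseline data. Trails, Verbal Fluency and Digit Coding are on the list of tests that define MCI, and they are also cognitive outcomes repeated at post-test, so the restriction needs to be written down.
3. A factor used to constrain the randomisation is left out of the primary model.

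The MCI group is also the only subgroup for which Section 14 highlights possible benefits (d of 0.25 or more on Trails A, Digit Symbol Coding and one TEA subtest, in 52 participants). Who belongs to it, and how that was decided, should be beyond question.

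**Working it through.** The plan gives no figure on this point to reproduce. The check sets the two codings side by side, then asks what the reported data can say about the size of any difference.

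**1. Where the codings can part**

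| Participant | Before randomisation (5.3, 6.3.2) | Aim 2 coding (9.6) |
|---|---|---|
| Clinic diagnosis of MCI, MoCA 26 or more | MCI by diagnosis | No MCI |
| Pilot replicate, MoCA 26 | Sent for evaluation under the cut-point then in force (27), so could be diagnosed with MCI | No MCI |
| MoCA 20–25, CDR and tests discordant | Physician's diagnosis | Adjudicated before final analysis |
| Clinic referral, MoCA 20–25 | Clinic diagnosis | Needs a CDR, which the study itself may not have collected |

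The pilot row matters only if pilot data are analysed, which Section 5.3 makes conditional on no significant procedural change afterwards.

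**2. Timing of the inputs.** Section 6.3.2 puts the clinical visit before randomisation. Section 6.1, speaking of baseline and clinical-visit measures together, says: "It will be allowable to administer any of the aforementioned measures that are missing from the baseline or clinical visits after randomization". It closes that window once training content has been received. A CDR obtained in that window could inform the Aim 2 coding but not the stratum.

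**3. What the MoCA figures show.** Inputs (Table 14.1): non-MCI mean 26.6 in both arms, SD 2.1 (piano) and 1.9 (listening). If every non-MCI participant scored 26 to 30, the largest possible SD would be

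√[(30 − 26.6) × (26.6 − 26)] = √(3.4 × 0.6) = 1.43,

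or 1.48 allowing for rounding of the mean and the sample-SD divisor. Both reported SDs exceed this, so some non-MCI participants scored 25 or less. The smallest fraction compatible with the means and SDs on a 20–30 scale, found by linear programming, is 3.3% of 96 (at least 4 people) and 2.0% of 97 (at least 2).

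**4. Arm sizes under the analysis coding.** These are inferred from the counts and percentages of women in Table 14.1, assuming truncated percentages (no group size gives 18 women as 48% under rounding) and a total of 268 (error df 266 + 2):

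- Non-MCI: 63/96 = 65.6% and 58/97 = 59.8%.
- MCI: 18/37 = 48.6% and 17/38 = 44.7%.
- Total: 96 + 97 + 37 + 38 = 268.

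The analysis groups are almost equal by arm.

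**5. Illustrative effect on the interaction.** Assume that the stratum is the true modifier and that a fraction e of 75 stratum-MCI participants is coded non-MCI, with no recoding the other way and no relation to arm. The 75 (37 + 38) and 193 (96 + 97) come from the analysis coding and stand in for the stratum sizes. The share of the contrast retained is 193 / (193 + 75e):

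- e = 5%: 193/196.75 = 0.981
- e = 10%: 193/200.5 = 0.963
- e = 20%: 193/208 = 0.928

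**6. Reported models.** Table 14.2 lists group, time, their interaction, hearing, visual acuity and expectations. MCI status is absent.

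**The case against.** The strongest reply is that nothing shows the two codings to differ in practice. The same kind of baseline information and the study physicians are involved both times, and only two discordant patterns are adjudicated. A moderator need not be a stratification factor. MCI was never randomised, and if status is coded from baseline data blind to arm, piano versus listening within each group remains a randomised comparison. Section 9.6 also has the merit of one explicit rule for all replicates, whereas the stratum's rule is unwritten and referral for evaluation moved from a MoCA of 26 or less to 25 or less. The clinic's own evaluation may well have included a CDR, and the referral route is optional. All of this stands, and it is why the stratum need not replace the Section 9.6 definition as the Aim 2 moderator.

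A reader might infer from the MoCA SDs that many participants were moved out of their stratum. The documents do not support that. Section 5.3 sends MoCA 20–25 scorers for evaluation to find out whether they have MCI. Someone judged not to have it before randomisation would be non-MCI in both codings. Any count beyond the minimum in the working would depend on an assumed shape for the scores, and even then would not count misplaced people. The near-equal arm sizes give no sign of large reclassification, although they do not prove that the codings agree.

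The reply does not answer the missing link between the codings, the missing safeguards on adjudication, or the absence of the stratum from every model. The personal names in Section 5.5 are removed, so whether the physicians were among those kept blind cannot be determined.

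**Conclusion.** The point holds as a gap in specification and safeguards, not as demonstrated bias. The plan has two procedures for MCI status, does not connect them, and leaves identifiable routes by which they can disagree. Adjudication is not stated to be blind or limited to data from before training. The stratum as randomised is not used in Aim 1, Aim 2 or any sensitivity analysis.

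The number of participants whose codings disagree is not given and cannot be derived; it could be zero. The 93–98% retention figures are an illustration under one-way recoding unrelated to arm, and they suggest modest attenuation at most in that range. They do not cover coding influenced by arm or outcome, which is the route the safeguards are meant to close. The change is worth making because it is cheap and because the affected subgroup is the one whose effects are highlighted, even though the three-way interactions were not significant.

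**What to change.** 1. **Aim 1 model:** add the MCI stratum recorded at randomisation and its interaction with time. The main effect alone would barely change the group-by-time estimate, because it explains differences in level rather than in change.
2. **Aim 2 definition:** keep the Section 9.6 rule. State that adjudication uses only data collected before training, is blind to arm and post-test results, and is locked before unblinding.
3. **Transparency:** cross-tabulate randomisation stratum by analysis status, by arm.
4. **Sensitivity:** repeat Aim 2 with the stratum as randomised.
5. **Consistency:** reconcile Section 6.1 (missing clinical-visit measures allowed after randomisation) with Section 6.3.2 (clinical visit before randomisation).

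At the planning stage the cost is SAP wording and one extra model run, since the stratum should already be on file. Because Section 14 already reports results, items 1, 3 and 4 now mean a refit and a supplementary table, and item 2 means documenting when adjudication was done, from which data, and with what knowledge of arm and outcome.
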